Identifying imaging and control pitfalls or possible delays introduced	The Butterfly US probe selected for this application was not suitable to train the sonographers and utilise the POC system for the data collection due to the probe overheating limiting the continuous scanning capabilities of the probe. Later a Philips US probe was used.  Delays in the scanning procedure which were related instead to the POC system were caused on several occasions by the robotic arm, the computers and the Haptic Touch controller, which needed to be restarted  •The robotic arm joints were overstressed, or an excessive pressure was applied on the robot	Robotic examination image acquisition efficiency was initially longer than image acquisition via traditional examination, however there was no difference in reporting time. A significant learning curve was identified regarding efficiency in image acquisition	Although there were delays seen in acquiring the images due to the different types of US probes used, the final combination of Jaco 2 arm and the chosen US probe has brought in significant improvements and acquisition timing similar to a manual scan

	
while mounting the probe on the probe holder;
 
 
•The cables connected to the Haptic Touch controller/screens/computers were stretched became disconnected from the corresponding device;
 
•The system froze, and rebooting was needed for unknown reasons.
 
		

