#### 11.1.1 Decision Criteria

The primary objectives of the study are to:

- assess the **safety** of the RUAT echo.
- assess the **“useability” (functionality)** of using the RUAT echo as intended to obtain echocardiogram images of clinically suitable quality for reporting by a cardiac sonographer.

The **safety** of the RUAT Echo will be considered acceptable if there are no device related adverse effects.

RUAT Echo will be considered a **useable** method of performing echocardiograms if:

- Each functional verification criteria 1 through 11 (inclusive) performed “YES” at least 80% of the time an echocardiogram was performed by RUAT Echo, that is, pass functional verification (see APPENDIX 1 - Functional Verification ).
- At least 80% of echocardiograms performed by RUAT Echo are considered of an adequate quality to provide a diagnostic assessment, that is, pass functional verification item #12 (see APPENDIX 1 - Functional Verification ).
- At least 80% of participants report they are satisfied with undergoing RUAT Echo examination based on an average of the 4 subscales of the 10-point Likert scales from strongly disagree to strongly agree (see APPENDIX 2 – Participant Survey).

	QMS Template	Doc ID: RMI-ROBOTECHO-CIP-002 Ver No: V2.0
	Clinical Investigation Protocol	

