### 11.1.4 Handling of Missing Data

Missing data will not be imputed.

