## 11.2 Analysis Sets

For the purposes of analysis, the following analysis sets are defined:

Participant Analysis Set	Description
Full analysis set (FAS)	All participants.
Safety analysis set (SAS)	All participants who are exposed to investigational medical device.

The full analysis set will be used to analyse endpoints related to the usability objectives and the safety analysis set will be used to analyse the endpoints and assessments related to safety.

All observed data will be used in the analysis.

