### 11.3.2 Useability (functionality)

The RUAT Echo device will be deemed as being **sufficiently useable (functional)** (i.e., technically non-inferior) **if each of the 12 Functional Verification Criteria** (see APPENDIX 1 - Functional Verification ) result in "YES"  $\geq 80\%$  of the time.

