## 23 Appendices

### 23.1 APPENDIX 1 - Functional Verification Checklist

#	Function	Performs as Intended (Y/N)
1	Did the Robotic Arm & cameras activate when turned on?	
2	Did the robotic arm move into home position when instructed?	

3	Did the robotic arm move into the preset positions correctly?	
4	Could the sonographer move the robotic arm onto the patient's chest from each preset position?	
5	Could the sonographer move the robotic arm from the end of the preset movement to the correct location on the patient's chest? (tests x,y, z axes).	
6	When in the correct location, could the robotic arm be instructed to the correct angulation so that an image could be acquired? (tests panning, tilting, rotation functionality).	
7	Did the force sensor work within its pressure range?	
8	Did the probe holder hold the probe correctly for the scan?	
9	Was there any restriction to the robotic arm movement caused by the cables? (wound around arm, caught in the bed, too short length from the US machine).	
10	Could the sonographer move the robot trolley as required during the scan?	
11	Did the patient telehealth screen provide adequate image and audio?	
12	Was the sonographer satisfied that the images could be used for reporting?	

	QMS Template	Doc ID: RMI-ROBOTECHO-CIP-002 Ver No: V2.0
	Clinical Investigation Protocol	

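### The useability pass rule counts only echocardiograms that were performed, an undefined term, while two other sections of the protocol imply a different denominator

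*Protocol*

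**What the plan says.** Three places in the protocol bear on the denominator of the useability rule.

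- **Section 11.1.1 (Decision Criteria).** Items 1 to 11 must each be met "at least 80% of the time an echocardiogram was performed by RUAT Echo". The item 12 rule is: "At least 80% of echocardiograms performed by RUAT Echo are considered of an adequate quality to provide a diagnostic assessment". Both are conditional on an echocardiogram having been performed, and the protocol does not say whether that means started, partly done or completed.
- **Section 11.3.2 (Useability).** The device is sufficiently useable if "each of the 12 Functional Verification Criteria" reach 80%. There is no condition that a scan was performed.
- **Section 11.2 (Analysis Sets).** "The full analysis set will be used to analyse endpoints related to the usability objectives", and that set is described as all participants. It adds: "All observed data will be used in the analysis".

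The checklist in Appendix 1 begins with steps that come before any imaging. Item 1 asks: "Did the Robotic Arm & cameras activate when turned on". Items 2 to 4 ask about the home position, the preset positions and reaching the chest.

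On sessions that fail, Section 11.1.3 calls intercurrent events not applicable and Section 11.1.4 says "Missing data will not be imputed". Section 13.1 rules out replacement after the RUAT echocardiogram has been received, and is silent on participants whose scan never took place. Section 13.2 withdraws participants who cannot tolerate the procedure, without saying how they count towards useability.

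**The concern.** The rule is meant to test whether the device works. Several checklist items test preconditions for obtaining any scan. If one of those steps fails outright, no echocardiogram results, and on the literal wording of Section 11.1.1 that session leaves the denominator. The most serious functional failures could then be left out of the functional verdict. For item 12 the same conditioning turns the share of participants who end up with reportable images into the share among those who could be scanned.

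Sections 11.2 and 11.3.2 point to an unconditional base, so the protocol contradicts itself on a primary pass/fail criterion. If this is not settled before data are seen, the denominator could be chosen afterwards, and the choice can decide the result.

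**Working it through.** **1. The plan's own figure.** Section 11.6 gives a two-sided 95% Clopper-Pearson interval for 24/30 = 80%. Lower limit: the 0.025 quantile of Beta(24, 7) = 61.4%. Upper limit: the 0.975 quantile of Beta(25, 6) = 92.3%. The width is 30.9 percentage points. This matches the protocol. It assumes that all 30 participants contribute; if 6 scans dropped out and 20 of the remaining 24 were adequate, the interval would be 62.6% to 95.3%.

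**2. Inputs.** From the protocol: up to 30 participants, one RUAT scan each, threshold 80% (24 of 30). Assumed, because the protocol gives no rate of failed or stopped RUAT sessions: the share *s* of attempts that yield a performed scan, and the share *q* of performed scans that are adequate.

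**3. Item 1, counts.** Suppose *f* of 30 sessions never start, are excluded under Section 11.1.1, and all others are YES.

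| f | Over performed scans | Over attempts |
|---|---|---|
| 6 | 24/24 = 100%, pass | 24/30 = 80.0%, pass |
| 7 | 23/23 = 100%, pass | 23/30 = 76.7%, fail |

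Up to 6 non-starts pass either way; from 7 the two readings disagree. Over 30 attempts, the chance of passing item 1 is P(X ≥ 24) with X ~ Bin(30, 1 − failure rate):

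| Start-up failure rate | Chance of passing over attempts |
|---|---|
| 5% | 0.999 |
| 10% | 0.974 |
| 25% | 0.348 |
| 40% | 0.017 |

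The denominator therefore matters for item 1 only if start-up failure is common.

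**4. Item 12, counts.** Fewer lost scans are needed. With 2 of 30 not performed and 23 adequate, 23/28 = 82.1% passes and 23/30 = 76.7% fails.

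**5. Item 12, chance of passing.** Take *q* = 0.90.

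- Over performed scans: sum over K ~ Bin(30, s) of P(adequate ≥ 0.8K), where adequate ~ Bin(K, 0.90).
- Over attempts: P(X ≥ 24), X ~ Bin(30, 0.90 × s).

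| s | Adequate per attempt, 0.90 × s | Over performed scans | Over 30 attempts |
|---|---|---|---|
| 0.95 | 85.5% | 0.95 | 0.87 |
| 0.90 | 81.0% | 0.95 | 0.66 |
| 0.85 | 76.5% | 0.95 | 0.42 |

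The conditional rule hardly responds to how often a scan could be obtained. The all-attempts rule responds strongly.

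**The case against.** The strongest reply is that the protocol as a whole does not exclude failed sessions. Section 11.2 puts useability on all participants and uses all observed data, and Section 11.3.2 has no performed condition. On those sections a recorded failure on item 1 counts even when no scan follows. That is correct, and it is why the finding is a contradiction and not a settled exclusion. It does not remove the problem: Section 11.1.1 is the section headed as decision criteria, and using observed data does not say how to score an item 12 that was never reached.

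A reader might infer that item 1 cannot fail. The documents do not support that. The arm or a camera could fail at first switch-on, be restarted, and the scan then go ahead with item 1 marked as a failure. Items 2 to 4 can also fail in a session that still yields images, for example if one preset position is wrong.

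A reader might also infer that stopped scans always drop out. Since performed is undefined and the observing sonographer is at the bedside, a partial scan could still be scored.

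Table 1 in Section 5.1 records that "The system froze, and rebooting was needed for unknown reasons", but for the earlier proof-of-concept device and as a cause of delay. The summary of the 78-participant COBOT study in Section 5.2 mentions no failed starts. The precedent shows that such failures are possible, not how often they would occur with RUAT.

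Finally, scoring of unreached items could be set out in the statistical analysis plan, and Section 11.1 already reports numbers tested and analysed, so lost sessions may be visible. Neither resolves a denominator that the protocol itself states in conflicting ways.

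**Conclusion.** The concern holds as an inconsistency with a direction. Section 11.1.1 conditions all 12 items on an undefined performed scan, Sections 11.2 and 11.3.2 do not, and the literal reading of Section 11.1.1 favours the device by allowing sessions in which it prevents a scan to be left out.

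The size depends on an unknown failure rate. For item 1 the readings part only at 7 or more non-starts in 30. For item 12, at 90% adequacy among performed scans, the gap in the chance of passing is 0.95 against 0.87 when 5% of scans are lost, and 0.95 against 0.42 when 15% are lost. These figures assume independent sessions and failures that prevent the scan altogether.

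This should be fixed before data are seen. In a descriptive pilot of 30 participants, with no failure rate documented for RUAT, it does not show that the verdict will be wrong.

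**What to change.** In Sections 11.1.1, 11.2 and 11.3.2, state one denominator for items 1 to 12: every participant with an attempted RUAT scan. Require the checklist in Appendix 1 to be completed at every attempt. Score as a failure any item not reached because the device failed or the scan was stopped, including item 12. Write failure and not NO, because item 9 asks about a restriction and a no there is the good answer. Report the numbers attempted, started and completed.

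The cost is a few sentences in Section 11 and one instruction on the checklist, with no extra participants. The reported percentages may be slightly lower than under the conditional reading.

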### 11.1.3 Impact of Intercurrent Events Strategies

Not applicable.

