**13.2 Subject Withdrawals**

Subjects will be withdrawn from the study if:

- Their consent is withdrawn.
- In the investigator’s opinion, the subject’s clinical condition necessitates withdrawal for safety reasons.
- They are unable to tolerate RUAT echocardiogram procedure.

Subjects will be advised that they may voluntarily withdraw from the study at any time, for any reason and they are not obligated to reveal the reason to the sponsor, and it will not affect their medical care. However, in such cases, appropriate efforts will be made by the sponsor to determine the reason for voluntary withdrawal from the study.

Subjects will be informed that should they withdraw from the study they should remain in the care of an appropriately experienced physician until the physician deems further follow-up unnecessary.

A Study Completion Form will be completed for all patients who withdraw from the study.

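### The 80% rules for checklist items 1–12 count performed scans, but usability is assigned to all participants, so attempted scans that fail can leave the denominator

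*Protocol*

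**What the plan says.** Protocol section 11.1.1 sets three usability rules, each with an 80% threshold.

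- Items 1–11 of the Appendix 1 checklist must each be YES "at least 80% of the time an echocardiogram was performed by RUAT Echo".
- Item 12 (images usable for reporting) is met if "At least 80% of echocardiograms performed by RUAT Echo are considered of an adequate quality to provide a diagnostic assessment".
- Satisfaction is met if "At least 80% of participants report they are satisfied with undergoing RUAT Echo examination".

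The first two rules count scans performed; the third counts participants. Performed is not defined.

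Section 11.3.2 restates the checklist rule as "technically non-inferior) if each of the 12 Functional Verification Criteria" being YES at least 80% of the time, with no mention of performed scans. Section 11.2 analyses usability in the full analysis set, defined as all participants, and uses all observed data.

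Three other sections bear on a scan that fails. Section 13.2 lists as a reason for withdrawal from the study: "They are unable to tolerate RUAT echocardiogram procedure". Section 11.1.4 states "Missing data will not be imputed". Section 11.1.3, on intercurrent events, reads in full "Not applicable". No section says how a stopped or never-started scan is scored.

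**The concern.** A scan abandoned because the arm faults, or because the participant cannot bear it, is a failure of usability. If such a scan is held not to have been performed, the failure disappears from the proportion that decides whether the device is usable, and the remaining scans look better than the device was.

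Item 1 shows the weakness most clearly: "Did the Robotic Arm & cameras activate when turned on" If the arm does not activate, there may be no performed echocardiogram against which to record the NO.

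Such events are foreseeable. Table 1 (section 5.1) reports restarts, freezing and subcostal discomfort with the proof-of-concept system, although that was a different robot. Section 12 tells participants that they may stop if probe pressure is too uncomfortable. At stake is whether two analysts holding the same data could reach opposite verdicts on a primary objective.

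**Working it through.** **Plan's own figure.** Section 11.6 takes n = 30, an observed 80% and a two-sided 95% Clopper-Pearson interval, and states 61.4% to 92.3%, width 30.9%. With x = 24, the lower limit is the 2.5% quantile of Beta(24, 7) and the upper limit is the 97.5% quantile of Beta(25, 6). This gives 61.43% to 92.29%, width 30.85%. The figure reproduces, and it takes all 30 participants as the base.

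**Which base applies.**

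| Section | Base for usability |
|---|---|
| 11.1.1, items 1–11 and item 12 | scans performed |
| 11.1.1, satisfaction | participants |
| 11.2 | all participants, all observed data |
| 11.3.2 | not stated |

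**Effect on the verdict.** Assume 30 attempted scans, of which k are not completed and drop out; k is an assumption, because the protocol gives no abandonment rate. The smallest passing count on performed scans is r = ceil(0.8 × (30 − k)). If the k scans stay in as NO, 24 of 30 are needed.

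| k dropped | Smallest pass, performed only | Same count over 30 | Verdict over 30 |
|---|---|---|---|
| 0 | 24/30 = 80.0% | 80.0% | pass |
| 1 | 24/29 = 82.8% | 80.0% | pass |
| 2 | 23/28 = 82.1% | 76.7% | fail |
| 3 | 22/27 = 81.5% | 73.3% | fail |
| 4 | 21/26 = 80.8% | 70.0% | fail |
| 5 | 20/25 = 80.0% | 66.7% | fail |
| 6 | 20/24 = 83.3% | 66.7% | fail |

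The verdicts differ only when the YES count lies between r and 23. For k = 2 that is exactly 23; for k = 5 it is 20 to 23, while 24 or 25 YES out of 25 passes both ways. The reported interval moves too: 20/25 gives 59.3% to 93.2%, and 20/30 gives 47.2% to 82.7%.

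**Chance of meeting the item 12 rule.** Let q be the probability that a scan is abandoned and p the probability that a completed scan is reportable, with scans independent. Both values are assumed.

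- Performed only: sum over n of P(Bin(30, 1 − q) = n) × P(Bin(n, p) ≥ ceil(0.8n)).
- Failures counted: P(Bin(30, (1 − q)p) ≥ 24).

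| q | p | Success per attempt, (1 − q)p | Performed only | Failures counted |
|---|---|---|---|---|
| 0 | 0.85 | 85.0% | 84.7% | 84.7% |
| 0.05 | 0.85 | 80.75% | 78.0% | 64.7% |
| 0.10 | 0.85 | 76.5% | 78.4% | 42.1% |
| 0.10 | 0.90 | 81.0% | 95.0% | 66.0% |
| 0.20 | 0.90 | 72.0% | 94.2% | 22.4% |

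On performed scans the chance of passing hardly responds to q, so that reading is almost blind to abandonment.

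**The case against.** The strongest reply is that exclusion is inferred and never stated. Section 11.2 puts all participants in the usability set and uses all observed data. Section 13.2 withdraws a participant but does not delete what was already recorded. Section 10.2.1.1 has the Observing Sonographer complete the checklist with no condition that the scan finished, and 11.3.2 restates the rule without the word performed. A stopped scan could therefore be entered as NO. The study is also a descriptive pilot, 13.1 expects every subject to complete, and technical detail is deferred to a statistical analysis plan.

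Much of this stands, and it rules out several stronger readings that a reader might infer:

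- *That the protocol excludes failed scans.* It permits that reading; it does not state it.
- *That all three usability rules are biased upward.* The satisfaction rule counts participants, and section 10.2 has each participant complete a survey at the end of the scan, which an early end may still satisfy. Section 10.2.1.2 ties delivery to completion, so the risk is missing surveys and no more.
- *That item 1 cannot fail.* It also covers the cameras, and nothing says that a camera fault prevents a scan.
- *That the safety criterion is tilted toward success.* The safety set keeps everyone exposed, events are collected from consent to 72 hours after the scan (10.3.2), and a sonographer is at the bedside. No event is shown to be lost. The protocol merely does not say that the 72-hour contact continues after withdrawal.

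The reply does not remove the conflict. Observed data cannot supply a checklist that was never completed, and all participants is not a precise base either, since it could include someone who never came to a session. The deferral does not help, because 11.1.1 itself fixes the decision rule and its denominator; an analysis plan that follows the protocol inherits both bases.

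**Conclusion.** The point holds as a conflict over the denominator that can change the pass decision. Sections 11.1.1 and 11.2 give different bases for items 1–12, and 11.1.3, 11.1.4 and 13.2 leave abandoned scans unresolved in a way that lets device failures drop out of the rule meant to detect them. Calling intercurrent events not applicable also sits badly beside a withdrawal criterion that names one.

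The size depends on an abandonment count that the protocol does not give. With 30 attempts, 0 or 1 dropped scan changes nothing and from 2 the verdict can flip. These counts assume that every abandoned scan is excluded and that the YES count is close to the threshold. If no scan is abandoned, the two readings agree.

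**What to change.** **Denominator and scoring (11.1.1, 11.2, 11.3.2).**

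- Define the denominator for items 1–12 as every participant in whom a RUAT session was attempted, including a session in which the system failed to switch on.
- Score a session not completed because of device fault or intolerance as NO on item 12 and on any item that failed. Say how items not reached are counted.
- For satisfaction, use the same set and the recorded answers wherever there is a survey. Count a participant as not satisfied only if no survey is available.
- Report performed-only proportions as supplementary.

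**Data collection (13.2 with 10.2.1, 10.3.2 and 11.1.3).** Reconcile these sections so that, consent permitting, the checklist, the survey and the 72-hour safety contact are still collected after a stopped scan. Replace the entry in 11.1.3 with a reference to the scoring rule. None of this changes when a scan is stopped.

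The cost is wording in the protocol and the analysis plan, settled before the data are reviewed, and a slightly less favourable pass rate. Counting non-completion as failure is not the only defensible choice, but it leaves one verdict per data set and keeps device failures in the rule.

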### 11.1.2 Multiplicity Adjustment

No adjustment for multiple comparisons is planned.

### 11.1.3 Impact of Intercurrent Events Strategies

Not applicable.

### 11.1.4 Handling of Missing Data

Missing data will not be imputed.

## 11.2 Analysis Sets

For the purposes of analysis, the following analysis sets are defined:

Participant Analysis Set	Description
Full analysis set (FAS)	All participants.
Safety analysis set (SAS)	All participants who are exposed to investigational medical device.

The full analysis set will be used to analyse endpoints related to the usability objectives and the safety analysis set will be used to analyse the endpoints and assessments related to safety.

All observed data will be used in the analysis.

## 11.3 Analyses Supporting Primary Objective(s)

### 11.3.1 Primary Endpoint(s)

The primary endpoints are as listed in Table 2.

#### 11.3.1.1 Definition of endpoint(s)

Adverse events, adverse device effects, serious adverse events and serious adverse device effects are defined in Section 10.3.

### 11.3.2 Useability (functionality)

The RUAT Echo device will be deemed as being **sufficiently useable (functional)** (i.e., technically non-inferior) **if each of the 12 Functional Verification Criteria** (see APPENDIX 1 - Functional Verification ) result in "YES"  $\geq 80\%$  of the time.

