#### 11.3.2.1 Main Analytical Approach

The proportion of RUAT echocardiograms deemed to be of sufficient quality will be summarised descriptively along with a 95% confidence interval.

Participant experience will be summarised descriptively.

Adverse events and serious adverse events will be coded using the Medical Dictionary for Regulatory Affairs and will be summarised by system organ class and preferred term by echocardiogram type (conventional vs RUAT Echo). No statistical comparisons between adverse events or serious adverse events by scan type are planned.

Adverse device effects will be coded using the FDA Medical Device Report (MDR) adverse event codes and will be summarised by Level 1 Term and Level 3 Term by echocardiogram type (conventional vs RUAT Echo).

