#### 11.6 Sample Size Determination

Approximately 30 participants will be recruited. A single-group design will be used to obtain a two-sided 95% confidence interval for a single proportion of the RUAT Echo images that are deemed of sufficient quality. The Exact (Clopper-Pearson) formula will be used to calculate the confidence interval. The sample proportion is assumed to be 80%. With a sample size of 30, the width of the associated confidence interval is 30.9% around the 80% (that is, from 61.4% to 92.3%).

Confidence interval widths were computed using PASS 2023, version 23.0.2.

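### Section 11.3.2 labels an observed 80% pass rate as technical non-inferiority, which a single-group descriptive pilot with no comparator, margin or confidence-bound rule cannot show

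*Protocol*

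**What the plan says.** - Protocol 11.3.2 makes the device sufficiently useable "if each of the 12 Functional Verification Criteria" is answered YES in at least 80% of scans, and glosses that outcome as "i.e., technically non-inferior".
- Protocol 11.1.1 sets the same bar. Items 1 to 11 must each have "performed “YES” at least 80% of the time an echocardiogram was performed by RUAT Echo", and for item 12, "At least 80% of echocardiograms performed by RUAT Echo are considered of an adequate quality to provide a diagnostic assessment". The conclusion there is only that the device is useable.
- Protocol 11.6 gives the design basis: "A single-group design will be used to obtain a two-sided 95% confidence interval for a single proportion". It adds "With a sample size of 30, the width of the associated confidence interval is 30.9% around the 80" per cent, with limits of 61.4% and 92.3%. It states no hypothesis, margin or power.
- Protocol 11.3.2.1 reports the image-quality proportion descriptively with a 95% interval. Conventional and robotic scans appear side by side only in the tables of adverse events and device effects, and no statistical comparison of adverse events is planned.
- Sections 3 and 8 call the study a pilot, and 11.1 says that data will in general be summarised descriptively.

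**The concern.** A non-inferiority conclusion says that a new method is not worse than a named reference by more than a stated amount, with the uncertainty accounted for. Section 11.3.2 attaches that conclusion to a rule that contains no reference, no amount and no allowance for uncertainty. This is protocol text that defines what a pass means, so it is not a detail that can wait for the analysis plan. No analysis plan could make it true, because the data needed for the comparison are not collected.

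Section 18 says that the study report may be used in regulatory applications. There, non-inferior has a specific inferential meaning. A pilot threshold carrying that label could be read as a demonstrated level of performance relative to manual echo.

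**Working it through.** **1. Is there a comparator for the checklist?** Appendix 1 asks about the robotic arm, its preset positions, the force sensor, the probe holder, cables, trolley and telehealth screen. Most of these have no counterpart in a manual scan. Item 12 (images usable for reporting) could have one, but no comparison is planned. Section 9.1 also admits only people whose manual echo has already been clinically reported, so the manual result is fixed as reportable by selection.

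**2. Is there a margin?** None is stated. As an illustration only, Section 5.2 gives manual-echo feasibility in the earlier study as 99% for structures and 97% for measurements. Against those rates, an 80% bar would imply margins of 99 − 80 = 19 and 97 − 80 = 17 points. Those endpoints differ from the checklist, and the protocol does not propose them as a reference.

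**3. Does the decision use a confidence limit?** No. Sections 11.1.1 and 11.3.2 compare an observed proportion with 80%. The planned interval for image quality is descriptive and is not linked to the decision.

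**4. Reproduce the plan's interval.** Inputs from 11.6: n = 30, observed proportion 80% (x = 24), "two-sided 95% confidence interval", Clopper-Pearson.
- Lower limit = Beta quantile(0.025; x, n − x + 1) = Beta quantile(0.025; 24, 7) = 0.6143
- Upper limit = Beta quantile(0.975; x + 1, n − x) = Beta quantile(0.975; 25, 6) = 0.9229
- Width = 0.3085

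This matches the stated 61.4%, 92.3% and 30.9%. The protocol gives the interval for image quality, but the arithmetic is the same for any item at 24/30.

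**5. How often does one item pass?** P(X ≥ 24), with X binomial(30, p):

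| True rate p | P(pass) |
|---|---|
| 0.65 | 0.06 |
| 0.70 | 0.16 |
| 0.75 | 0.35 |
| 0.80 | 0.61 |
| 0.85 | 0.85 |
| 0.90 | 0.97 |

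**6. What would a confidence-bound rule need?** For the lower two-sided 95% limit to exceed 80% with n = 30, 29/30 is required (lower limit 82.8%); 28/30 gives 77.9%. The chance of at least 29/30 is 0.18 at a true 90% and 0.55 at a true 95%. The first sample size giving at least 80% power on one item is 107, 69 or 41 for assumed true rates of 90%, 92% or 95%. Even that rule would test against a fixed performance level and not against manual echo.

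**The case against.** The strongest reply is that this is one loose parenthesis in an openly descriptive pilot. Section 11.3.2 defines its term operationally, the study is sized for interval width, and *technically* may mean only that the robot does what its manual says. Section 11.6 already prints the 61.4% limit, so nothing is hidden. Much of this stands: the defect is a label, and an observed-rate threshold is acceptable in a pilot. It does not rescue the label, because the operational definition contains no comparison.

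A reader might infer more than the document supports, in four ways.

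- *The rule is too lenient.* The figures in step 5 are for one item, and all 12 must pass. If every item had a true rate of 80%, the chance that all pass would be 0.607^12 = 0.0025 under independence and 0.61 under perfect dependence. At 85% the corresponding figures are 0.14 and 0.85. The document says nothing about dependence, and items 3 to 6 are successive movements of one arm, so no single figure is defensible. A strict joint rule is still not a comparison with manual echo.
- *The other results will be reported without intervals.* For the survey, 11.3.2.1 says "Participant experience will be summarised descriptively", which does not exclude intervals. Section 11 defers technical detail to an analysis plan that is not at hand.
- *The threshold or the sample size is wrong.* Neither follows. For a pilot that reports observed rates, both can stand.
- *The report will claim non-inferiority.* Section 18 says only that a report may support applications. The risk comes from the wording; it is not a stated intention.

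**Conclusion.** The point holds as a wrong statement in the protocol. Meeting an observed 80% on each checklist item cannot establish non-inferiority, technical or otherwise, and 11.3.2 should not say that it does. The protocol is also inconsistent with itself, since 11.1.1 draws only the conclusion of useable from the same thresholds.

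In size, an item that just passes at n = 30 is compatible with a true rate of about 61%, and an item with a true rate of 70% passes about one time in six. These figures assume that exactly 30 scans are evaluated (the protocol says up to, or approximately, 30), that scans are independent with a common rate, and that YES counts as success. Item 9 is worded so that a literal YES describes a fault, so it must be scored as performing as intended for the last assumption to hold. The conclusion that the label is unsupported depends on none of these assumptions.

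**What to change.** In 11.3.2, delete the parenthesis containing "i.e., technically non-inferior" and bring the sentence into line with 11.1.1. For example: *The device will be considered useable on functional verification if, for each of the 12 items, the observed rate met the pilot threshold of 80%.* If 11.3.2 instead cross-refers to 11.1.1, note that 11.1.1 also includes a participant-satisfaction criterion that 11.3.2 does not list.

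The threshold, the sample size and the figures in 11.6 do not change. The cost is a one-line amendment and a more modest claim. Keeping the non-inferiority wording would instead require a reference, a justified margin, a rule on a confidence limit and a re-sized study.

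As an optional addition for the analysis plan, and not part of the error, exact 95% intervals could be reported for the other checklist items, satisfaction and device-related adverse events.
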